Data Structure: There are two key unique features of the primary data for this proposal. First, because couples are enrolled in the study, there is inherent nesting of two individuals within each couple. Second, the measurement design leads to repeated measurements outcomes for some of the aims. Given the aims of the study, many of the outcomes will be evaluated using descriptive statistics. However, issues such as nesting and repeated measurements will be carefully considered. For example, for the first aim, uptake will be reported by each individual within the couple, and the descriptive statistics will be reported both at the individual level within the couple and at the aggregate couple level. For the outcomes that will be evaluated using inferential statistical analyses, the nested data structures (e.g., repeated measurements within couples) will be addressed using mixed-effects regression models (MRMs; e.g.).⁸¹ These highly flexible models accommodate variability in the number/spacing of outcome measurements, and they readily accommodate linear and non-linear outcome distributions (e.g., dichotomous, count). **Outcome Distributions & Individual Trajectories:** Prior to analysis, each outcome will be carefully inspected to determine the most appropriate distribution for modeling. Likewise, for outcomes with repeated measurements, the trajectory for each participant on each outcome will be plotted using “spaghetti plots”.⁸² These plots will illustrate the level of and variability in each outcome, along with patterns of change over time. **Model Building & Estimation:** Singer and Willett’s (2003)⁸³ model building approach will be used to specify fixed and random effects. The MRMs will be performed using MLwiN software.⁸⁴ Due to the relatively modest sample size for some of the analyses, the models will also be performed using Bayesian MCMC-based estimation⁸⁵ in MLwiN. This simulation-based approach utilizes a large number of iterations – each informing the next – to produce an empirically-based sampling distribution for each parameter. For example, rather than a single point estimate of the parameter of interest, the MCMC-based provides the magnitude, precision, and variability of the parameter estimates. **Attrition & Missing Data:** Individuals or couples who drop out of clinic care will be retained, when possible, in ongoing research measurement according to Intention-to-treat principles.⁸⁶ Some research data will inevitably be missing, and the methods recommended by Schafer and Graham⁸⁷ will be used to evaluate missing data assumptions and guide the subsequent analyses. Given few missing data and evidence supporting a MAR mechanism, the procedures detailed above will be utilized with all available data. Given non-trivial missing data and evidence supporting MAR, multiple imputation for longitudinal data will be used to provide complete data.⁸⁸ Finally, given non-trivial missing data and evidence suggesting NMAR, pattern mixture models will be used to control the missing data.⁸²

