
Evaluation of Specific Aims & Associated Hypotheses

AIM 1 - We hypothesize that the majority of couples (GT ~ 50%) will utilize the HIV self-test kits and share their results with their partner. To evaluate the factors associated with uptake of HIV self-testing, a single level logistic regression model with a logit link function will be performed. The outcome will be the HIV self-testing status (0 = did not use self-test, 1 = used self-test). Demographic variables (e.g., age & gender) will be evaluated as predictors of self-testing uptake, with results focusing on ORs, and corresponding 95% CIs.

AIM 2 - We hypothesize that a large proportion of serodiscordant couples who present to the study referral office (GT ~ 70%) will engage in care together, have higher rates of adherence and retention than individually enrolled clients, and have a reduction in risk behaviors for HIV transmission from baseline to 18-month follow up. For this aim, there are repeated measurements of retention in care and adherence (level-1) nested within positive partners (level-2). A dichotomous predictor variable at the individual level (i.e., level-2) will test for differences in the log-odds of treatment retention between those enrolled in care as a couple and those enrolled in routine clinic services. The adherence outcome will be analyzed in a similar manner. For this outcome, there are several indicators of medication adherence. First, for the positive member of the couples, self-reports of ARV adherence will be obtained at 6, 12, and 18 months. Second, individuals on ARV are expected to return to the clinic each month to have the prescription refilled. Third, for individuals in the study, viral load tests will be obtained at 18 months allowing us to assess viral suppression as a marker for medication adherence. For the

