Precision of Estimates and Statistical Power: The level of precision and statistical power is necessarily limited given the stage of the research and the sample size associated with many of the outcomes. For the descriptive statistics, the margin of error was computed as an indicator of the level of precision afforded by the sample.

For AIM 1 – Based on our review of available literature on the prevalence of HIV sero-discordancy in stable couples we estimate that we will need to enroll approximately 442 couples to yield enough serodiscordant couples (N=60) to enroll in the second phase of the study. However, this is an uncertain estimate, and it may require up to 1000 couples. The expected percentage of the sample that will opt to use the HIV self-test is 50%-70%. The widest margin occurs at the level of 50%; therefore, this value was selected. With a sample of 442 and self-test use of 50%, the 95% confidence interval for the true value of this estimate is 46% to 54%. With a sample of 1000 and self-test use of 50%, the 95% confidence interval for the true value of this estimate is 48% to 52%.

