For AIM 2 - For the estimated sub-sample of 50 individuals for the PrEP use outcome, the 95% confidence interval for 50% PrEP use is 36% to 64%. If this percentage is as high as 75%, the confidence interval would be 63% to 87%. For the MRMs, this sample is sufficient for accurate estimates of fixed effects.⁸⁹ Although the point estimates of variance components and SEs could be biased, the proposed Bayesian MCMC-based analyses will provide increasingly valid estimates and will provide information about the variability and precision of the estimates.⁸⁵ Also of note, with the current design, the primary statistical test (i.e., that a time-varying correlation = 0) has a much smaller sample size requirement than does the primary statistical test for a traditional randomized design (i.e., between-group difference in slopes = 0). Statistical power was estimated using the method recommended by Maas and Hox⁸⁹ for a design with a level-1 predictor variable, a random intercept, and no other random effects. The lower limit on power is provided by the outcomes with 3 research measurement occasions, and outcomes utilizing clinic data and samples will offer much higher statistical power. With an estimated 50 individuals and 3 measurement occasions, the level-1 sample size is 150. Penalizing this sample for a nesting effect characteristic of repeated measurement data, ICC = .50, the effective level-1 sample size is 75 (i.e., given the dependence in the data, the level-1 sample of 150 offers the power of a sample of 75). For the dichotomous outcome and the dichotomous level-1 predictor, with an effective level-1 sample of 75, power is .80 to detect an event rate of 30%

(i.e., OR = 4.26). Assuming up to a 20% loss to follow-up rate, we will enroll 60 couples to ensure there are at least 150 measurements in total.

In sum, with between 442 and 1,000 couples in the HIV self-testing component of the study, and between 60-70 couples in the Dyadic Care component of the study we estimate that we will have adequate statistical precision and power to answer the requisite study questions.

TIMELINE – Based on experience working in the area we feel confident we can meet these goals:

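### Aim 1 precision: 442 and 1,000 couples give 95% intervals of 45%-55% and 47%-53% at 50% uptake, not the printed 46%-54% and 48%-52%, and neither unit nor adjustment is stated

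*Combined protocol and SAP*

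**What the plan says.** In Section D, Precision of Estimates and Statistical Power, the Aim 1 paragraph estimates that about 442 couples must be enrolled to find 60 serodiscordant couples, and adds that "it may require up to 1000 couples". Expected uptake is 50% to 70%, and the worst case is taken: "The widest margin occurs at the level of 50%; therefore, this value was selected". Two intervals follow:

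- "With a sample of 442 and self-test use of 50%, the 95% confidence interval for the true value of this estimate is 46% to 54" per cent.
- "With a sample of 1000 and self-test use of 50%, the 95% confidence interval for the true value of this estimate is 48% to 52" per cent.

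The section describes its precision measure only as a margin of error. For Aim 1 it names no design effect, ICC or finite-population correction, and does not say whether the sample consists of couples or persons.

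Other sections point to different units. The Data Structure part of the Analysis Plan says of Aim 1 uptake that "the descriptive statistics will be reported both at the individual level within the couple and at the aggregate couple level". The Aim 1 hypothesis concerns couples: "the majority of couples (GT ~ 50%) will utilize the HIV self-test kits". The opening study summary equates 442 and 1,000 couples with 884 and 2,000 individuals.

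**The concern.** Read as written, the samples are 442 and 1,000 couples, and the intervals are narrower than those numbers allow. They are the only precision figures for Aim 1 uptake, and the closing sentence of the power section relies on 442 to 1,000 couples for its claim of adequate precision.

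The hypothesis sets uptake against about 50% of couples. From the printed intervals a reader would infer that observed uptake of about 54% (442) or 52% (1,000) puts the lower 95% limit above 50%. At couple level without adjustment it takes about 54.7% and 53.1%. Because uptake is to be reported at two levels, the reader also cannot tell which level the intervals describe.

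**Working it through.** **Inputs.** p = 0.50, 95% two-sided (z = 1.96), and n = 442 and 1,000, all from the Aim 1 precision paragraph. Also 884 and 2,000 individuals (opening summary), ICC = 0.50 (Aim 2 precision paragraph, stated there for repeated measurements), and 3,101 households in the ward (Community Selection).

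**Formula.** Half-width = 1.96 × √(p(1−p)/n).

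**Check on the section's own figures (Aim 2, n = 50).**
- p = 0.50: 1.96 × √(0.25/50) = 0.1386, giving 36% to 64%. The plan says "the 95% confidence interval for 50% PrEP use is 36% to 64" per cent.
- p = 0.75: 1.96 × √(0.1875/50) = 0.1200, giving 63% to 87%, as printed.

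The plain formula therefore reproduces both Aim 2 intervals. That outcome has one person per couple, so this does not prove which formula was used for Aim 1.

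**Aim 1 with the stated n.**
- n = 442: 1.96 × √(0.25/442) = 0.0466, giving 45.3% to 54.7% (rounds to 45%-55%).
- n = 1,000: 1.96 × √(0.25/1000) = 0.0310, giving 46.9% to 53.1% (rounds to 47%-53%).

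Wilson intervals (45.36-54.64 and 46.91-53.09) and exact intervals (45.24-54.76 and 46.85-53.15) round the same way.

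**Rounding.** Limits of 46%-54% and 48%-52% allow half-widths of at most 4.5 and 2.5 points.
- n needed for 4.5 points: 0.25 × (1.96/0.045)² = 474.3, so 475.
- n needed for 2.5 points: 0.25 × (1.96/0.025)² = 1,536.6, so 1,537.
- Shortfall in half-width: 1 − 4.5/4.66 = about 3%, and 1 − 2.5/3.10 = about 19%.

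**Can values given in the document rescue both intervals?** For two persons per couple the design effect is 1 + ICC. The finite-population factor is √((N−n)/(N−1)).

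| Reading | Lower sample | Upper sample | Both match? |
|---|---|---|---|
| Couples, unadjusted | 45.3-54.7 | 46.9-53.1 | Neither |
| 884 / 2,000 individuals, no clustering | 46.7-53.3 | 47.8-52.2 | Second only |
| Individuals, ICC 0.50 | 46.0-54.0 | 47.3-52.7 | First only |
| Couples, finite population of 3,101 households | 45.7-54.3 | 47.4-52.6 | First only |
| Couples, 90% level instead of 95% | 46.1-53.9 | 47.4-52.6 | First only |

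**Which assumptions would match both?**
- Individuals with a within-couple ICC of about 0.13 to 0.30. At 0.20 the half-widths are 3.61 and 2.40 points.
- Couples with a finite-population correction for about 1,306 to 2,861 eligible couples. At 2,000 they are 4.12 and 2.19 points.

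The document gives neither an ICC for self-test use nor a count of eligible couples.

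**Uptake needed for the lower limit to exceed 50%.** Solving p − 1.96 × √(p(1−p)/n) = 0.50 gives p of about 0.547 at n = 442 and 0.531 at n = 1,000.

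**The case against.** The strongest reply is that individuals were meant. The Aim 1 regression codes use of the test as yes or no, with age and gender as predictors, which are person-level variables. The Data Structure text has uptake reported by each member of the couple. With 2,000 people and no clustering, the interval is 47.8% to 52.2%, which is the printed 48%-52%. The interval with the larger apparent error would then be right, and the one for 442 slightly wide.

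This is a plausible reading, and it is why no single slip can be named. It does not rescue the pair. 884 individuals give 47%-53%, not 46%-54%, and allowing for clustering with the only ICC in the section repairs the first interval but breaks the second. If individuals were intended, the n and the clustering assumption are missing from the plan, which is itself part of the concern.

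It is also fair to say that little depends on this. At 442 the gap after rounding is 4.66 − 4.5 = 0.16 points, and 1,000 is the upper end of a contingency range. The hypothesis is approximate and no test against 50% is planned. The 50% threshold is a way of showing the size of the error, not a decision rule in the plan. The final intervals will come from the data. All of this stands, and it limits the severity without making the printed figures correct.

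**Conclusion.** The concern holds and is minor. For couples with no adjustment, which is what the paragraph states, the intervals are 45% to 55% and 47% to 53%. At face value the printed limits are too narrow by about 0.7 points per side at 442 (4.66 − 4) and 1.1 points at 1,000 (3.10 − 2). With rounding fully in the plan's favour, 0.16 and 0.60 points remain.

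Confidence is high that the printed pair cannot be reproduced from the stated inputs. Calling 45%-55% and 47%-53% the correct replacements depends on couples being the unit and on no adjustment being intended. Sample size is unaffected, because the 442 to 1,000 range comes from the expected yield of serodiscordant couples. A margin of 3 to 5 points remains suitable for a descriptive study.

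**What to change.** In the Aim 1 precision paragraph, restate the couple-level intervals as 45% to 55% for 442 couples and 47% to 53% for 1,000 couples, and say that the unit is the couple. If individual-level or finite-population-adjusted precision was intended, state the n with the within-couple ICC or the number of eligible couples, and recompute both intervals. Since uptake will be reported at both levels, giving one labelled interval for each would remove the ambiguity. The cost is two corrected intervals and one clause naming the unit, with no change to enrolment or analysis.

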AIM 3 - We hypothesize that a moderate proportion of HIV negative partners will utilize PrEP (~ 30%), that PrEP utilization among HIV negative partners will be associated with lack of ARV use by positive partners, and ARV use by positive partners will be associated with lack of PrEP use by negative partners. To evaluate the factors associated with uptake of PrEP, a single level logistic regression model with a logit link function will be performed. Demographic variables such as age and gender will be evaluated as predictors of PrEP uptake, with the results focusing on the odds ratios, and corresponding 95% confidence intervals, for these variables. To evaluate association between ARV and PrEP utilization within couples, two main models will be performed. For the first, the outcomes will be variables related to the use of PrEP. Likewise, for the second, the outcomes will be variables related to the use of ARV. These outcomes will be evaluated using MRMs as described above. Because each outcome is specific to one member of the couple (i.e., the negative partner for PrEP and the positive partner for ARV), the data will have a two level structure with repeated measurements (level-1) nested within couples (level-2). At the repeated measurements level of the model, the partner's ARV or PrEP status for the preceding time period will be entered as a time-varying covariate. For example, for the PrEP outcome, the positive partner's ARV status will be entered at level-1, and this will test for differences in the use of PrEP for negative partners whose positive partners were on ARV versus not on ARV. Similarly, for the ARV outcome, the negative partner's PrEP status will be entered at level-1, and this will test for differences in the use of ARV for positive partners whose negative partners were on PrEP versus not on PrEP. More tailored formulations are also possible. For example, introducing a lag between the predictor and outcome could test the extent to which PrEP and ARV status were associated with later initiation of ARV or PrEP. **We hypothesize couples will alternate risk reduction strategies (abstinence, ARV treatment for the positive partner, PrEP for the negative partner, and condom use) but typically maintain at least one strategy.** Each risk reduction strategy will be considered as a separate outcome, with repeated measurements of strategies (level-1) nested within couples (level-2). The model specification will be heavily informed by preliminary evaluation of the spaghetti plots, as described above. These plots will guide tests for patterns of change over time (e.g., linear), specific phases of change, or even invariance over time such that aggregation is justified. After building the mixed-effects model, predictor variables related to the use of abstinence, condoms, ARV, or PrEP will be added to the model. These variables will also be considered for entry as time-varying covariates (i.e., entry at level-1) or as aggregative, couple-specific predictors based on the findings of the previous models. Such a formulation will test for, for example, differences in the use of risk reduction strategies for time periods when the positive partner is on ART versus not on ART. Based on the descriptive statistics and the patterns of use of each individual strategy over time, supplemental analyses will be considered that simultaneously evaluate all of the strategies. For instance, cluster analyses could be used to identify groupings of individuals based on the combination of risk reduction strategies utilized.

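### The penalty that cuts 150 measurements to 75 fits a partner status that never changes, so .80 power at OR 4.26 is not the power of the time-varying test that the plan specifies

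*Combined protocol and SAP*

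**What the plan says.** The calculation is in the Analysis Plan of the combined protocol and SAP, under Precision of Estimates and Statistical Power, AIM 2. That paragraph names "the primary statistical test (i.e., that a time-varying correlation = 0") and says power was estimated "for a design with a level-1 predictor variable, a random intercept, and no other random effects". The inputs are then given: "With an estimated 50 individuals and 3 measurement occasions, the level-1 sample size is 150"; next, "Penalizing this sample for a nesting effect characteristic of repeated measurement data, ICC = .50, the effective level-1 sample size is 75"; and finally, for a dichotomous outcome and a dichotomous level-1 predictor, "with an effective level-1 sample of 75, power is .80 to detect an event rate of 30" percent, expressed as an OR of 4.26.

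The model is described under Evaluation of Specific Aims & Associated Hypotheses, AIM 3. Repeated measurements are nested within couples, and at the repeated-measurement level "the partner's ARV or PrEP status for the preceding time period will be entered as a time-varying covariate".

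The power paragraph does not state how far partner status is correlated over time within a couple, how common each status is, alpha or sidedness, whether the OR is marginal or conditional on the random intercept, or what the 30% refers to.

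**The concern.** The divisor 1 + (m − 1) × ICC measures the information lost when a predictor takes the same value on every occasion in a cluster. A predictor that changes between occasions is partly compared with itself inside the couple, where the random intercept cancels, so its loss is different. The power section itself argues that a time-varying test needs far fewer observations than a between-group one, and then applies the between-cluster penalty.

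This is the only model-based power figure in the plan, and the section goes on to conclude that power is adequate. It is therefore the figure against which a null finding on the ARV–PrEP association in Aim 3 would be read. If it describes a different test, so does the detectable effect of 4.26.

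**Working it through.** **Inputs from the plan:** n = 50 couples, m = 3 occasions, ICC r = .50, OR 4.26, stated power .80, 30% event rate. **Assumed, because not stated:** two-sided alpha .05, an even split of partner status unless noted, and ρx varied from 0 to 1.

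**1. Reproducing 75.** 150/[1 + (3 − 1)(.50)] = 150/2 = 75, exactly.

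**2. Reproducing .80.** An ordinary two-proportion calculation with 37.5 observations per predictor level gives:
- 30% as the overall rate (15.7% vs 44.3%): .78
- 30 points as the difference (17.5% vs 47.5%): .80
- 30% as the reference rate (30% vs 64.6%): .87
- 30% as the reference rate, lower direction (30% vs 9.1%): .63

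The first two readings are within 2 points of the stated value; the last two are not. The overall-rate reading is used below.

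**3. Effective n for a level-1 predictor (linear-model basis).** For a random-intercept model:

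n_eff = n × [m − r(m + m(m − 1)ρx)/(1 + (m − 1)r)]/(1 − r)

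= 50 × [3 − .5(3 + 6ρx)/2]/.5 = 225 − 150ρx.

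This is the sum of a within-couple part, 200(1 − ρx), and a between-couple part, 25(1 + 2ρx). It equals 75 only at ρx = 1, where the within-couple part is zero.

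| ρx | n_eff | Power at OR 4.26 | OR detectable at .80 |
|---|---|---|---|
| 1 | 75 | .78 | 4.42 |
| .9 | 90 | .85 | 3.83 |
| .75 | 112.5 | .92 | 3.29 |
| .5 | 150 | .975 | 2.78 |
| 0 | 225 | .998 | 2.29 |

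**4. The random-intercept logistic model.** The outcome is binary, so step 3 is only an approximation. Expected Fisher information for a random-intercept logistic model (50 × 3, latent-scale ICC .50, overall rate 30%, even split) gives:

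| ρx | Power if 4.26 is marginal | Power if 4.26 is conditional |
|---|---|---|
| 1 | .78 | .50 |
| .9 | .80 | .53 |
| .75 | .84 | .58 |
| .5 | .88 | .65 |
| 0 | .94 | .75 |

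The columns differ because, under these inputs, a conditional OR of 4.26 corresponds to marginal rates of 20.2% and 39.8%, a marginal OR of (.398/.602)/(.202/.798) = 2.61.

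**5. Sensitivity to prevalence.** With 30% as the reference rate and a conditional OR of 4.26, power runs from .53 (ρx = 1) to .80 (ρx = 0) at an even split, and from .37 to .62 if 80% of partner observations have the status.

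**6. Information on within-couple change alone.** On the linear basis, 200(1 − ρx) is 100, 50 and 20 at ρx = .5, .75 and .9.

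**The case against.** The strongest defence is that the error is on the safe side. Aim 3 enters partner status uncentred, so the coefficient blends between-couple and within-couple differences. On the effective-n basis the plan uses, 75 is the minimum of 225 − 150ρx over ρx from 0 to 1. If status seldom changes, 75 is also nearly right: 90 at ρx = .9. The study is exploratory, and the plan admits that power is limited. All of this stands on the linear basis. It does not settle the matter, because the planned model for a dichotomous outcome estimates a conditional OR and the plan does not say that 4.26 is anything else.

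Three stronger readings are tempting, and the documents do not support them.

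- *The study is underpowered.* Step 4 gives .78 to .94 on one OR scale and .50 to .75 on the other, and the documents do not choose between them.
- *The primary test has very low power because few couples switch.* The small effective samples in step 6 belong to a within-couple effect that the plan does not specify as its coefficient, and ρx appears nowhere. Immediate ARV access and recruitment from patients already in care make stable ARV status plausible, but do not quantify it.
- *The plan wrongly calls 75 a worst case.* Its remark about the lowest power concerns outcomes with three occasions as against monthly clinic data. It makes no claim about the clustering penalty.

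**Conclusion.** The mismatch is certain: the penalty is that of a couple-constant predictor, and the test is on a time-varying one. The direction of the resulting error is not fixed. For the blended coefficient on the plan's own linear-model basis, 75 and OR 4.26 are conservative (at ρx = .5, effective n 150 and a detectable OR of about 2.8). If 4.26 is conditional, .80 overstates power, which is about .50 to .75 at a 30% overall rate with an even split. For within-couple change the figure says nothing, and little information remains if partner status rarely changes.

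These sizes rest on the assumed alpha, split, ρx and reading of the 30%. The conclusion that the stated figure does not describe the stated test does not depend on them.

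**What to change.** State in the power section that an effective sample size of 75 applies to a partner status that is constant over time. Replace the .80/OR 4.26 figure with power, or detectable ORs, simulated from the planned random-intercept logistic model with 50 couples, 3 occasions and ICC .50, for assumed ρx of .5, .75 and .9. Report alongside:
- whether the OR is marginal or conditional, and the scale on which the ICC is defined;
- the assumed prevalence of partner ARV and PrEP status;
- alpha and sidedness;
- what the 30% event rate refers to.

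If a within-couple effect is to be interpreted, give its detectable OR separately. The expression 225 − 150ρx should not go into the protocol as exact, since it comes from a linear model and the outcome is binary.

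The cost is a recalculation and revised wording, with no change to enrolment or data collection. The price is that the restated figure may be less favourable than .80.

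### Sixty couples do not guarantee 150 measurements at 20% loss: if lost couples give no follow-up visit, 144 remain (minor)

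*Combined protocol and SAP*

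**What the plan says.** All the figures are in Section D, under Precision of Estimates and Statistical Power, in the paragraph for Aim 2. The plan takes 50 individuals at 3 measurement occasions, which is 150 level-1 records. It reduces this to an effective 75 for an ICC of .50. It then states that "with an effective level-1 sample of 75, power is .80 to detect an event rate of 30" percent, given as an odds ratio of 4.26. The method is said to be "for a design with a level-1 predictor variable, a random intercept, and no other random effects". Next to that stands the sentence "The lower limit on power is provided by the outcomes with 3 research measurement occasions", which contrasts these outcomes with those that use clinic data. The paragraph ends with the enrolment figure: "Assuming up to a 20% loss to follow-up rate, we will enroll 60 couples to ensure there are at least 150 measurements in total".

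For PrEP use the same paragraph gives precision only. It opens with "For the estimated sub-sample of 50 individuals for the PrEP use outcome" and reports a 95% interval of 36% to 64% around 50% use. The model for predictors of uptake is under AIM 3 in the Evaluation of Specific Aims: "To evaluate the factors associated with uptake of PrEP, a single level logistic regression model with a logit link function will be performed". Its results are to be reported as odds ratios with 95% confidence intervals.

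The section opens with a caveat, "The level of precision and statistical power is necessarily limited given the stage of the research", and closes by concluding that "we will have adequate statistical precision and power to answer the requisite study questions".

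**The concern.** The enrolment sentence promises a minimum number of measurements at any loss up to 20%. A promise of that kind has to hold at 20% itself, whenever the couples are lost. The number 60 looks like 50 increased by 20%. Increasing by 20% does not offset a later loss of 20%.

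The second matter is the reach of the closing sentence. The only power figure in the plan is for a time-varying predictor with repeated records per couple. The PrEP-uptake model has one record per negative partner, fewer than the effective 75. If the closing sentence is taken to include that model, a null result for a predictor of uptake could be reported as adequately powered evidence of no association.

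**Working it through.** **Inputs from the plan.** 60 couples enrolled (up to 70 allowed), loss up to 20%, 3 follow-up occasions (6, 12 and 18 months), 50 analysable individuals, ICC .50, OR 4.26, event rate 30%, stated power .80, expected PrEP uptake about 30%.

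**Assumed, because the plan does not state them.** Two-sided alpha of 0.05, an even split of the predictor, and the comparison rate that goes with OR 4.26.

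**1. Reproduce the plan's own figures.**
- Records: 50 × 3 = 150.
- Effective n = 150 / [1 + (3 − 1) × 0.50] = 150 / 2 = 75. This agrees.
- Power at effective n 75, two-proportion test. Two readings come close to .80:
  - 30% vs 64.6% (OR 4.26 applied to 30%), with continuity correction: .81.
  - 15.7% vs 44.3% (OR 4.26 with 30% overall), uncorrected: .78.
- The uncorrected test of 30% vs 64.6% gives .87. It does not reproduce the plan's figure and is not used below.

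**2. Check the guarantee.**
- 60 × 0.80 = 48 couples, and 48 × 3 = 144 measurements, 6 short of 150.
- Effective n = 144 / 2 = 72. Power falls from .81 to .79 on the first reading and from .78 to .76 on the second, about 2 points.
- Source of the 60: 50 × 1.2 = 60. Correct inflation: 50 / 0.80 = 62.5, so 63 couples (63 × 0.80 × 3 = 151.2).
- Largest whole-couple loss at which 60 couples still give 150: 1 − 50/60 = 16.7%.
- Loss accruing evenly to 20% at 18 months: 56 + 52 + 48 = 156.
- Break-even: the 12 lost couples have 12 × 3 = 36 possible visits. Six of these, half a visit per lost couple, restore 150.

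**3. What the .80 does not cover.** The PrEP-uptake model has one record per negative partner. The plan gives no effect size for uptake predictors, so OR 4.26 is borrowed from the power paragraph. The CI uses SE(log OR) = √(sum of 1/expected cell count) with n/2 per group at 15.7% and 44.3%, and limits 4.26 × exp(±1.96 × SE).

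| n | Power, 30% vs 64.6%, corrected | Power, 30% overall | SE(log OR), 30% overall | 95% CI around OR 4.26 |
|---|---|---|---|---|
| 75 (plan's effective n) | .81 | .78 | – | – |
| 50 | .59 | .60 | 0.681 | 1.1–16.2 |
| 60 | .69 | .68 | 0.622 | 1.3–14.4 |
| 70 | .77 | .75 | – | – |

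The intervals use 30% overall uptake because that is what AIM 3 expects. With an even split, 30% vs 64.6% would imply (30 + 64.6)/2 = about 47% overall.

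**The case against.** On the guarantee, the shortfall needs all 12 lost couples to miss every follow-up visit, and that is unlikely. The Analysis Plan (Attrition & Missing Data) keeps people who leave clinic care in research measurement when possible. The study supplies phones and records alternative contact methods, and phone surveys were already approved. Enrolment may also reach 70 couples, and from 63 upward the target is met even in the worst case. All of this stands, and it is why the point is minor. None of it turns 60 couples into a guarantee, because retention when possible is not certain and the sentence rests on 60.

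On power, a reader might infer that the plan claims .80, or a lower limit on power, for the PrEP-uptake model. The documents do not support that. The .80 is expressly tied to a level-1 predictor in a random-intercept model, and the lower-limit sentence naturally ranks outcomes within that family. For PrEP use the plan offers an interval, and for its predictors odds ratios with intervals. The section opens by calling precision and power limited, and the plan describes the study as exploratory. What is left is one closing sentence that is too general.

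A reader might also infer that the second part of the study is too small and should enrol more couples. A difference of 3 in effective sample size does not support that.

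**Conclusion.** The guarantee is wrong as written. At 20% loss before any follow-up visit, 60 couples give 144 measurements (effective n 72), about 2 points of power below the stated figure. With evenly accruing loss they give about 156, and the plan's target is met. This part rests only on the plan's own numbers and on when couples are lost.

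The closing adequacy statement reaches further than the calculations behind it. The single-level PrEP-uptake model has no stated power. The comparison of dyadic with routine care in Aim 2 uses a level-2 predictor, so it also lies outside the level-1 power calculation. For PrEP uptake, at the borrowed OR of 4.26, power is about .59–.60 at n = 50, .68–.69 at n = 60 and .75–.77 at n = 70. These figures depend on the assumed alpha, sidedness and predictor split, and on readings that only roughly reproduce .80 at 75.

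Severity is minor. No design feature, visit or model changes.

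**What to change.** 1. In the Aim 2 power paragraph, replace the guarantee with: Enrolling 60 couples gives 144 measurements (effective n 72) if 20% of couples are lost before any follow-up visit, and about 156 if loss accrues evenly.
2. Limit the closing sentence of the section to the analyses whose precision or power was computed, and say that the .80 applies to level-1 predictors in the repeated-measure models.
3. Under AIM 3, label the single-level PrEP-uptake model as estimation only, reported with the odds ratios and 95% intervals already planned. If a power figure is added, use the values in the table above, and state the alpha, the predictor split and that the OR is borrowed.

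The cost is wording only: no extra couples, visits or data. The plan gives up a guarantee it cannot keep and a general claim of adequacy.
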